7.3. Analysis of the Primary Efficacy Parameter

7.3.1. Primary Efficacy Analysis

An MMRM will be fitted for the comparisons between INCB018424 1.5% BID and vehicle cream based on percentage change from baseline in EASI scores to Week 2 and Week 4. The MMRM will include the fixed effect of treatment (the 4 dose levels of INCB018424 cream, active control, and vehicle cream), the randomization stratification factor (baseline EASI score of ≤ 7 or > 7), the visit, and treatment by visit interaction. The variance-covariance matrix of the within-subject errors in MMRM will be modeled as unstructured.

A test for superiority between INCB018424 1.5% BID and vehicle cream will be performed using the least squares mean estimate of the percentage change from baseline in EASI at Week 4 from the MMRM specified above. Superiority will be established if the p-value of the difference (INCB018424 1.5% BID minus vehicle) is less than 0.05.

The MMRM implicitly adjusts for missing data through a variance-covariance structure.

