9.4.1.2. Primary Efficacy Analyses

Comparisons between INCB018424 1.5% BID and vehicle based on percentage change from baseline in EASI scores at Week 4 will be performed with a fixed-effect ANOVA model using last observations carrying forward in the ITT.

The ANOVA model will include the fixed effects of treatment and randomization stratification factor. If there are no data after the date of randomization, then the endpoint will be considered missing and will not be included in analysis.

Supportive analyses for the primary endpoint include a similar ANOVA approach in the per protocol population.

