3.2. Control of Type I Error

For the primary endpoint and key secondary endpoints, the overall 2-sided Type I error rate is 0.05.

A graphical procedure with a gatekeeping testing strategy for the primary and key secondary analyses, as specified in Protocol Section 9.2.1, will be implemented to control the overall Type I error rate. The underlying procedure is derived using the methodology developed in Bretz et al (2009). This method will guarantee a strong control of the FWER.

A family of 7 elementary hypotheses, corresponding to treatment comparisons between active dose groups and vehicle (or triamcinolone) is evaluated in [Figure 1](#) based on the percentage change from baseline to Week 4 EASI score.

Figure 1: Illustration of the Statistical Treatment Comparisons

AC = active control; s = superiority; ni = noninferiority; V = vehicle.

Note: Active control (triamcinolone 0.1% cream) BID for 4 weeks followed by vehicle cream BID for 4 weeks.

The primary endpoint will test the superiority of INCB018424 1.5% BID compared with vehicle.

The key secondary endpoint has 2 branches. Branch 1 will test whether:

- INCB018424 1.5% BID is noninferior to triamcinolone (active control)
- INCB018424 1.5% QD is noninferior to triamcinolone (active control)
- INCB018424 1.5% BID is superior to triamcinolone (active control)
- INCB018424 1.5% QD is superior to triamcinolone (active control)

Branch 2 will test whether:

- INCB018424 1.5% QD is superior to vehicle
- INCB018424 0.5% QD is superior to vehicle

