3.2.1. Primary Analysis

The primary alternative hypothesis (superiority of INCB018424 1.5% BID compared with vehicle) will be tested at a 2-sided $\alpha = 0.05$ level. The test on the primary endpoint will be used as a gatekeeper for 6 statistical tests on secondary endpoints that will be grouped into 2 parallel branches (see [Figure 1](#)). The first branch (Branch 1) includes tests of INCB018424 versus the active control (triamcinolone). The second branch (Branch 2) includes tests of INCB018424 versus vehicle. The initial allocation of the overall significance level to Branch 1 and Branch 2 is 3/5 and 2/5, respectively. The weights of the level to be passed on if 1 hypothesis is rejected are specified in [Figure 1](#).

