7.4.1. Efficacy Analysis for Key Secondary Endpoints

The efficacy analysis for key secondary endpoints includes the 6 comparisons if the primary null hypothesis is rejected. Each comparison will be analyzed using a similar MMRM to that specified for the primary analysis. The graphical approach as specified in [Figure 1](#) will be used to control the FWER.

Four tests for superiority of 1 of the INCB018424 doses to active control or vehicle cream will be performed using the least squares mean estimate of the percentage change from baseline in EASI at Week 4 from the MMRM model specified above. Superiority will be established if the p-value of the difference (INCB018424 minus the reference group, either active control or vehicle) is less than the alpha level determined by the graphical procedure.

For noninferiority, tests comparing each of 2 INCB018424 treatment groups (1.5% BID and 1.5% QD) to the active control group will be performed using the least squares mean estimate of the percentage change from baseline in EASI at Week 4. Noninferiority will be established if the lower limit of a 2-sided CI for the difference (INCB018424 minus active control) is higher than or equal to -10%. The level of the corresponding CI will be determined by the graphical procedure. In addition, a CI with the usual 95% level will be reported.

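### The EASI models use baseline EASI only as a two-level stratum; adding the continuous value would probably give a modest precision gain at almost no cost

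*SAP*

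**What the plan says.** SAP 7.3.1 models "percentage change from baseline in EASI scores to Week 2 and Week 4". Baseline severity enters the model only as "the randomization stratification factor (baseline EASI score of ≤ 7 or > 7". The other fixed effects are treatment, visit and their interaction, with an unstructured covariance matrix. There is no continuous baseline EASI term.

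The same covariates carry to the six key secondary comparisons. SAP 7.4.1 states: "Each comparison will be analyzed using a similar MMRM to that specified for the primary analysis". With the primary test these make up "A family of 7 elementary hypotheses" (SAP 3.2).

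The ANOVA models are no different. Protocol 9.4.1.2 says "The ANOVA model will include the fixed effects of treatment and randomization stratification factor", and the LOCF ANOVA in SAP 7.3.3 uses the same two terms. No planned treatment comparison on percentage change in EASI therefore uses continuous baseline EASI as a covariate.

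SAP 7.2.1 defines percentage improvement with baseline EASI as the denominator, so the value must exist for every subject who has an outcome. Protocol 3.1 and 5.1.2 set entry limits on IGA (2 to 3) and BSA (3% to 20%) but no lower limit on EASI. The documents do not report the baseline EASI distribution, the split between strata, or the correlation of baseline with percentage change.

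**The concern.** A cut at 7 treats a subject at 7.1 and a subject at 20 as the same. If percentage change depends on baseline severity within a stratum, that dependence stays in the residual variance, and chance within-stratum imbalance among six arms of about 50 adds noise to the estimates. The continuous value is already in the database and could remove some of this.

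The stake is precision. It matters most for the noninferiority test of 1.5% BID against triamcinolone, because that test is the first step of Branch 1 and the other three tests in the branch wait on it.

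**Working it through.** **Inputs from the documents**
- SD 13% and 50 per arm, 300 in all (Protocol 9.2 and 9.2.3).
- Assumed Week 4 improvements: vehicle 30, triamcinolone 50, 1.5% BID 75, 1.5% QD 65, 0.5% QD 50 (Protocol Table 5).
- Noninferiority margin -10 points (SAP 7.4.1).
- Overall two-sided alpha 0.05. The starting split, "Branch 1 and Branch 2 is 3/5 and 2/5, respectively", gives 0.03 and 0.02.
- No dropout rate is stated and none is applied.

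**Assumptions**
- Correlation ρ between baseline EASI and percentage change: 0 to 0.5.
- Share q of subjects with EASI ≤ 7: 0.2 to 0.5.
- Baseline roughly normal and linearly related to outcome.
- The 13% is taken as the SD with only the stratum in the model.

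**Step 1. Reproduce the plan's power.** SE of a difference = 13 × √(2/50) = 2.60.
- Superiority to vehicle, differences 45, 35 and 20: the smallest gives 20/2.60 = 7.7 standard errors. Power is above 99.9% at 0.05, 0.03 and 0.02, so the stated figure of more than 99% reproduces.
- Superiority to triamcinolone, differences 25 and 15: 15/2.60 = 5.8 standard errors. Power is above 99.9% at 0.03, against a stated 95% or more.
- Noninferiority at a true difference of 0: 10/2.60 = 3.85 standard errors. Power is 97.0% (normal) or 96.8% (noncentral t) at 0.05, and 95.3% or 94.8% at 0.03. Protocol 9.2.3 states more than 99%, which does not reproduce. That is a separate matter, but it shows that noninferiority is where precision can still count.

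**Step 2. How much the cut already captures.** The share of a linear baseline signal held by the stratum is f = φ(z_q)² / [q(1 − q)].
- q = 0.5: 0.3989²/0.25 = 0.637.
- q = 0.2: 0.2800²/0.16 = 0.490.

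**Step 3. What the continuous term adds.** Variance ratio = (1 − ρ²)/(1 − fρ²), and the SE scales with its square root. Example at ρ = 0.3, q = 0.5: 0.91/(1 − 0.637 × 0.09) = 0.965, and 2.60 × √0.965 = 2.555.

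| ρ | q | Variance ratio | SE | Change in SE |
|---|---|---|---|---|
| 0.1 | 0.5 | 0.996 | 2.595 | -0.2% |
| 0.3 | 0.5 | 0.965 | 2.555 | -1.8% |
| 0.3 | 0.2 | 0.952 | 2.537 | -2.4% |
| 0.5 | 0.5 | 0.892 | 2.456 | -5.6% |
| 0.5 | 0.2 | 0.855 | 2.404 | -7.5% |

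At ρ = 0 the only effect is the lost degree of freedom. Residual df goes from 300 − 7 = 293 to 292, so the SE rises by √(293/292) − 1 = 0.17%.

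**Step 4. Cross-check by simulation** (Week 4 linear model, six arms of 50, complete data, 2,000 replications). When baseline explains about 0%, 2%, 9% or 18% of variance, mean SE goes from 2.600 to 2.605, 2.619 to 2.607, 2.670 to 2.609, and 2.743 to 2.601. That is +0.2%, -0.5%, -2.3% and -5.2%. The estimated difference stays at about 45.

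**Step 5. Effect on power.** Noninferiority, true difference 0, two-sided 0.03, noncentral t:

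| Further variance removed | Power |
|---|---|
| 0% | 94.8% |
| 2% | 95.2% |
| 3.5% | 95.5% |
| 6% | 96.0% |
| 10% | 96.7% |

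At the extreme of the assumed range (ρ = 0.5, q = 0.2) the normal formula goes from 95.3% to 97.7%, a gain of 2.4 points. Under Table 5 the noninferiority distance for 1.5% QD is (15 + 10)/2.60 = 9.6 standard errors, so power is effectively 100% with or without the term.

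**Step 6. If the SD is larger.** With an illustrative SD of 20 and a within-stratum correlation of 0.3 (9% variance cut), noninferiority power at 0.03 goes from 61.8% to 66.2%. Superiority of 1.5% QD to triamcinolone goes from 93.8% to 95.7%.

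**The case against.** A reader might infer that the plan discards baseline EASI and that all seven comparisons are therefore less precise. The documents do not support that.
- A gain needs a within-stratum association between baseline and percentage change, and none is reported. The outcome is already divided by baseline, so the association could be near zero, and the SE would then be about 0.2% larger.
- The stratum keeps about half to two-thirds of a linear baseline signal (49% to 64%), so the model uses baseline in part.

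A reader might also expect a large gain. A long-tailed lognormal baseline with ρ = 0.5 gives a variance reduction of up to 17%. With median 7 and log-SD 0.8, however, it puts 8.5% of subjects above EASI 21, which Protocol 7.6.1 labels severe, in a trial of mild to moderate disease. If baseline is limited to 21 or below, the reduction is 3.1-3.6% at ρ = 0.3 and 9.9-11.3% at ρ = 0.5.

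Randomization keeps chance imbalance from biasing the estimates, and the SE already reflects it. The MMRM already conditions on the Week 2 response when data are missing, and no dropout rate is given. Better support for the missing-at-random assumption is therefore possible but not shown. The form of the term is also a choice: a linear EASI term, log EASI and the stratum alone are all valid.

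These points limit the size and certainty of the gain, and they stand. They do not remove the case for the change. Dividing by a baseline measured with error tends to create a correlation rather than remove one. Simulating that mechanism alone (multiplicative error of 10-30% at both visits) gave correlations of about 0.07 to 0.26, though only 0.1-1.8% further variance removed. The sponsor also stratifies on EASI and plans a subgroup analysis by it (SAP 7.3.2), which suggests that it regards baseline EASI as relevant to outcome.

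**Conclusion.** The point holds as a modest, nearly free improvement in precision. Every planned model for percentage change in EASI uses baseline only as a two-level factor, and the seven comparisons are likely, but not certainly, somewhat less precise for it. For correlations of 0 to 0.5 and 20% to 50% of subjects at EASI ≤ 7, the SE changes by about +0.2% to -7.5%. At a correlation of 0.3, noninferiority power at a true difference of zero gains roughly one percentage point. No power figure under the Table 5 effects moves. The gain would be larger if the true SD exceeds 13%.

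It would be wrong to read this as an error in the primary analysis. The model is valid, it matches the randomization, and it controls Type I error as intended. Confidence is high on the omission and the low cost. It is low on the size of the gain, because the correlation is assumed.

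**What to change.** In SAP 7.3.1, and through it 7.4.1, add continuous baseline EASI and its interaction with visit to the MMRM. In SAP 7.3.3, add continuous baseline EASI to the LOCF ANOVA. Keep the randomization stratum in all of them, and state the scale of the covariate (for example, raw EASI) in advance.

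Make the change before any treatment assignment is unblinded. SAP section 9 lets some sponsor personnel see unblinded efficacy results at the interim analysis, so the wording should be final before then.

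The cost is about one line of SAP text and 1 degree of freedom (2 with the by-visit term). No new data are needed, no alpha is spent, and no subject is lost, because the outcome cannot be computed without baseline EASI. The worst case is an SE about 0.2% larger.

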7.3.2. Subgroup Analyses

Subgroups will be formed based on the following baseline variables for those subjects whose data are available:

- EASI score (0 to 7 and > 7 to 72);
- Baseline facial involvement (No/Yes)
- Serum IgE (> 200 kU/L, < 200 kU/L)

7.3.3. Sensitivity and Supportive Analyses for Primary Endpoint

A fixed-effect ANOVA model will also be performed for the comparisons between INCB018424 1.5% BID and vehicle cream based on percentage change from baseline in EASI scores to Week 4. Missing observations will be imputed by the last observations carrying forward in the ITT. The ANOVA model will include the fixed effects of treatment and randomization stratification factor.

The primary endpoint will be analyzed using the PP population as a sensitivity analysis to the ITT population in the DB period.

If the proportion of subjects with missing values for the primary endpoint is greater than 5% of the ITT population, extended models based on missing not at random assumption may be conducted for sensitivity analysis in ITT population.

7.4. Analysis of the Secondary [REDACTED] Efficacy Parameters

Secondary efficacy analyses will be conducted for the ITT population in the DB period.

7.4.1. Efficacy Analysis for Key Secondary Endpoints

The efficacy analysis for key secondary endpoints includes the 6 comparisons if the primary null hypothesis is rejected. Each comparison will be analyzed using a similar MMRM to that specified for the primary analysis. The graphical approach as specified in [Figure 1](#) will be used to control the FWER.

Four tests for superiority of 1 of the INCB018424 doses to active control or vehicle cream will be performed using the least squares mean estimate of the percentage change from baseline in EASI at Week 4 from the MMRM model specified above. Superiority will be established if the p-value of the difference (INCB018424 minus the reference group, either active control or vehicle) is less than the alpha level determined by the graphical procedure.

For noninferiority, tests comparing each of 2 INCB018424 treatment groups (1.5% BID and 1.5% QD) to the active control group will be performed using the least squares mean estimate of the percentage change from baseline in EASI at Week 4. Noninferiority will be established if the lower limit of a 2-sided CI for the difference (INCB018424 minus active control) is higher than or equal to -10%. The level of the corresponding CI will be determined by the graphical procedure. In addition, a CI with the usual 95% level will be reported.

7.4.2. Efficacy Analysis for Other Secondary Endpoints

There will be no adjustment for multiple comparisons for secondary endpoints other than the key secondary endpoints.

[figure not shown]
Mean, change from baseline, and percentage change from baseline of EASI scores to Week 2, Week 4, and Week 8 may be analyzed with the similar MMRM for the primary endpoint. EASI scores at visits other than those covered by the primary and key secondary endpoints will be summarized by treatment and visit using descriptive statistics.

Categorical endpoints, including the percentage of subjects achieving EASI-50 and the percentage of IGA responders at postbaseline visits, will be summarized by treatment and visit using descriptive statistics and may be analyzed by logistic regression with stratification factor of randomization (ie, EASI \leq 7 or $>$ 7). All nonresponders in the DB period, as well as all subjects who discontinue study treatment at any time before the timepoint of interest, or discontinue from the study for any reason, will be defined as nonresponders for the NRI analysis.

An E_{\max} model will be fit for assessment of the dose-response relationship on percentage change from baseline of EASI scores at Week 4, which will provide estimates of the maximum and minimum response levels; ED_{50} (the concentration where the response is the midpoint between the maximum and minimum); and the slope parameter. The 5 dose levels of INCB018424 cream in the model fitting will be vehicle, 0.15% QD, 0.5% QD, 1.5% QD, and 1.5% BID (equivalent to 3% QD).

The Kaplan-Meier product limit method will be used to estimate time to EASI-50. Treatment comparisons may be performed using the log-rank test stratified by randomization stratification factor, if applicable.

Daily Itch NRS scores will be summarized by treatment and visit using descriptive statistics as a continuous endpoint. Itch NRS scores for baseline and Weeks 2, 4, 8, 10, and 12 will be determined by averaging the daily NRS for the days from the start to the end of window as described in [Section 7.2.2](#). In addition, daily NRS Itch scores, from Day -7 to Week 4 will be summarized by treatment group and presented graphically.

8. SAFETY AND TOLERABILITY

8.1. General Considerations

The analyses in this section will be provided for the safety population in the DB period and for the open-label evaluable population in the open-label period. Summary tables may be replaced with listings when appropriate. For instance, an AE frequency table may be replaced with a listing if it only contains a few unique PTs reported on relatively few subjects. Unless otherwise stated, table summaries will be limited to AEs occurring within 30 days of the last application of study treatment or the first application in the open-label period (if available) of the study, whichever is earlier.

8.2. Adverse Events

8.2.1. Adverse Event Definitions

A TEAE is any AE either reported for the first time or worsening of a pre-existing event after the first application of study treatment. Adverse events will be considered treatment-emergent if they first occurred or worsened in severity after the first application of study treatment and on or before the date of the last visit of the period. Maximum severity from previous period(s) will be considered as the baseline severity for TEAEs.

Treatment-emergent AEs will be allocated to the study period (DB or open-label) according to the rules specified in [Table 5](#).

Table 5: Allocation of Treatment-Emergent Adverse Events to Study Period

Study Period	Treatment Group	First Application Date	Last Visit	Identification of Maximum Severity
DB period	All groups	Date of first application	Date of last visit in DB period	Maximum severity from baseline
Open-label period	INCB018424 cream 1.5% BID	Date of first application in DB period	Date of last visit in open-label period	Maximum severity from baseline
	INCB018424 cream 1.5% QD 0.5% QD 0.15% QD Vehicle triamcinolone	Date of first application in the open-label period	Date of last visit in open-label period	Maximum severity from baseline and DB period

Analysis of AEs (as discussed below) will be limited to TEAEs, but data listings will include all AEs regardless of their timing in relation to study treatment.

Adverse events will be tabulated by MedDRA PT and SOC. Severity of AEs will be described and graded using the NCI CTCAE v4.03. The CTCAE reporting guidelines and grading details are available on the Cancer Therapy Evaluation Program website.

Adverse events will be tabulated by the MedDRA PT and SOC. A grading (severity) scale is provided for each AE term as follows: (1) mild, (2) moderate, (3) severe.

The subset of AEs considered by the investigator to be related to study treatment (INCB018424 cream, vehicle cream, or triamcinolone cream) will be considered to be treatment-related AEs. If the investigator does not specify the relationship of the AE to study medication, the AE will be considered to be treatment-related. The incidence of AEs and treatment-related AEs will be tabulated. In addition, SAEs will be tabulated.

Any missing onset date, causality, or severity must be queried for resolution. Unresolved missing values will be handled according to the following rules:

- An unresolved missing causality will be considered treatment-related.
- An unresolved missing severity will be identified as an unknown severity.

For purposes of analysis, all AEs will be considered TEAEs unless the AE can unequivocally be defined as not treatment emergent.

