6.5. Follow-Up

After the EOT visit (Weeks 8 or 12, or early termination), subjects will have follow-up assessments 1 month later to monitor for durability of effect (relapse rate), AEs, medication history, vital signs, and clinical assessments. If prohibited treatment for AD is started, an earlier follow-up visit may be performed. A final and thus end-of-study visit should be performed ideally no earlier than 30 days after the last dose of study drug. Adverse events and SAEs must be reported up until at least 30 days after the last dose of study drug, the date of the follow-up visit, or until toxicities resolve, return to baseline, or are deemed irreversible, whichever is longer. If needed, a follow-up phone call will be conducted to determine any AEs or SAEs during the 30 days after the last dose of study drug. Reasonable efforts should be made to have the subject return for the follow-up visit and report any AEs that may occur during follow-up.

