9.4.2. Safety Analyses

9.4.2.1. Adverse Events

A treatment-emergent AE (TEAE) is any AE either reported for the first time or worsening of a pre-existing event after first dose of study drug. Analysis of AEs will be limited to TEAEs, but data listings will include all AEs regardless of their timing to study drug administration. Adverse events will be tabulated by the MedDRA preferred term and system organ class. Severity of AEs will be based on the National Cancer Institute CTCAE v4.03 using Grades 1 through 4.

The subset of AEs considered by the investigator to have a relationship to study drug will be considered to be treatment-related AEs. If the investigator does not specify the relationship of the AE to study drug, then the AE will be considered treatment-related. The incidence of AEs and treatment-related AEs will be tabulated.

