3. STUDY DESIGN

This is a randomized, vehicle- and active (triamcinolone 0.1% cream)-controlled study in subjects with mild to moderate AD. The study is double-blinded for vehicle, INCB018424 doses, and active control. Approximately 300 subjects will be randomized 1:1:1:1:1:1 (approximately 50 subjects each) to treatment with INCB018424 1.5% BID, INCB018424 1.5% QD, INCB018424 0.5% QD, INCB018424 0.15% QD, vehicle BID, and active control (triamcinolone 0.1% cream) BID and stratified by EASI score (≤ 7 and > 7). Subjects will receive blinded study drug for 8 weeks. Subjects randomized to QD regimens will apply vehicle for the evening application. Subjects randomized to triamcinolone will apply triamcinolone 0.1% cream BID for 4 weeks and vehicle cream for 4 weeks to not exceed the allowable triamcinolone application duration.

After the DB period, a 4-week period of open-label treatment with INCB018424 1.5% cream BID will be offered to subjects who meet Protocol-defined criteria. Subjects will have follow-up assessments 1 month after the last application of study drug. The total duration of participation will be up to 20 weeks, including up to 4 weeks for screening, 8 weeks of DB treatment, 4 weeks of optional open-label treatment, and 4 weeks of safety follow-up.

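### SAP 8.2.1 ends treatment-emergence at the last visit of the period, so an adverse event dated after that visit is literally left out of tables that SAP 8.1 limits only at 30 days after the last application

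*SAP*

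**What the plan says.** SAP 8.2.1 defines a treatment-emergent AE (TEAE) twice. Its opening sentence has no end date and follows Protocol 9.4.2.1, which covers "any AE either reported for the first time or worsening of a pre-existing event after first dose of study drug". The next sentence adds one: the event must first occur or worsen "after the first application of study treatment and on or before the date of the last visit of the period". Table 5 repeats the bound by period. For the double-blind (DB) row it is "Date of last visit in DB period", and the open-label rows have the matching entry. The section then restricts the tables: "Analysis of AEs (as discussed below) will be limited to TEAEs, but data listings will include all AEs".

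SAP 8.1 uses a different marker. "Unless otherwise stated, table summaries will be limited to AEs occurring within 30 days of the last application of study treatment", or the first open-label application if that is earlier.

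Protocol 8.1.2 asks for monitoring of new AEs for at least 30 days after the last dose. Protocol 6.5 adds that, if needed, "a follow-up phone call will be conducted to determine any AEs or SAEs during the 30 days after the last dose".

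The SAP does not say whether the follow-up visit is a visit of the DB or open-label period. SAP 3 lists the parts of participation separately: "8 weeks of DB treatment, 4 weeks of optional open-label treatment, and 4 weeks of safety follow-up". SAP Table 1 points the other way, since it lets the DB last available value reach 30 days after the last DB dose. Finally, SAP 8.2.1 treats every AE as treatment-emergent unless it is unequivocally not.

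**The concern.** Two rules set different end dates for one set of tables. Where the last visit comes before the 30-day limit, the last-visit rule decides, and events the protocol sets out to collect are not tabulated.

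The clearest case is a subject who has an AE between visits, stops the drug because of it and never returns. The event is dated after the last visit, so on the literal definition it is not a TEAE. It is then missing from the planned table of TEAEs leading to permanent discontinuation. An AE learned only through the Protocol 6.5 phone call is lost in the same way. The same logic reaches an event that begins after the last visit and is fatal before another.

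Safety and tolerability is a stated objective and endpoint. With about 50 subjects per arm, one subject missing from a table is 1/50 = 2 percentage points.

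**Working it through.** The plan states no figure to reproduce. The check compares the two end dates.

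**Inputs**
- Limit under SAP 8.1: L + 30, where L is the day of the last application (no open-label entry).
- Limit under SAP 8.2.1 and Table 5: V, the day of the last visit of the period.
- Follow-up visit (Protocol synopsis and Table 2): 30 ± 7 days after the last dose, so day +23 to +37.
- Week 4 visit: Day 28 ± 3. Week 8 visit: Day 56 ± 7 (Protocol Table 2).

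**Formula:** days lost = max(0, L + 30 − V).

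**Reading A: the follow-up visit is outside the period**
- Week 8 or end-of-treatment (EOT) visit on the day of last dose: 30 days lost.
- EOT visit 7 or 14 days after last dose (assumed): 30 − 7 = 23, or 30 − 14 = 16.
- As a share of calendar time, for a subject ending at Week 8: 30/(56 + 30) = 34.9%.
- For an open-label completer from the five switching arms, counted from open-label start: 30/(28 + 30) = 51.7%.
- For the DB row of a subject who enters open label, SAP 8.1 itself stops at the first open-label application, so little or nothing is lost there.

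**Reading B: the follow-up visit counts as the last visit**
- Held at day +23: 30 − 23 = 7 days lost.
- Held at day +30 or +37: 0 days lost.

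**Reading C: drug stopped and no later visit of any kind**

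The days below are assumed. The result does not depend on whether a follow-up visit would have counted.
- Visit Day 14, AE Day 18, last dose Day 20: the SAP 8.1 limit is Day 50 and the SAP 8.2.1 limit is Day 14. Days lost: 50 − 14 = 36 (36/50 = 72%), of which 6 are on treatment. The Day 18 event is excluded.
- Week 4 visit Day 28, last dose Day 42: 14 on-treatment + 30 post-dose = 44 days.
- Extreme within the visit windows, Week 4 visit Day 25 and last dose Day 62: 37 + 30 = 67 days.

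**With a single 30-day end date:** 0 days are lost under every reading.

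These are shares of calendar days, not of events. Nothing in the documents converts one to the other.

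**The case against.** Most of the case on the other side is sound, and it limits the point.

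- **The cutoff is the last visit, not the drug stop.** A reader might infer that all AEs after a subject stops drug disappear. They do not: an event between stopping and an attended EOT visit stays in.
- **Follow-up may belong to the period.** SAP Table 1 gives the DB period 30 post-dose days, and SAP 5.2 presents results only for the DB and open-label periods. If follow-up visits never counted, the 30-day limit in SAP 8.1 would rarely bind. On this reading the loss is 0 to 7 days for attenders. It is plausible, but the SAP does not state it.
- **SAP 8.1 is a cap.** It sets a maximum, unless otherwise stated. It does not promise that tables run to 30 days. But SAP 8.2.1 is then the rule stated otherwise, so the last-visit bound still governs.
- **The SAP is inconsistent rather than plainly exclusionary.** The opening definition in SAP 8.2.1 has no end date, and doubtful AEs default to TEAE. The default is not a clear rescue, because a fully dated onset after the last visit is plainly outside the bounded definition.
- **The no-return case needs several misses.** Protocol 5.5.2 calls for the EOT visit and for safety follow-up, and an unscheduled visit might also count. Even so, Protocol 6.4 and 6.5 rely on reasonable efforts, and Protocol 6.5 provides for a phone call.
- **No data are destroyed.** Listings keep every AE, including separate listings for AEs leading to discontinuation, serious AEs and fatal AEs. The AE analyses are descriptive, so no hypothesis test is affected.

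**Conclusion.** The point holds as a contradiction between SAP 8.1 and SAP 8.2.1 with Table 5, made worse by an undefined term. Taken literally, a dated AE after the last visit of the period is left out of the tables and kept in the listings.

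The size depends on the reading. It is up to 30 post-dose days if the follow-up visit is outside the period, for subjects who do not enter open label or who end it. It is 0 to 7 days for attenders if that visit counts. For a subject with no later visit it is every day after the last visit, including on-treatment days, under either reading.

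Two stronger inferences are not supported. One is that a material number of events will be lost: the documents give no rate of missed EOT and follow-up visits and no AE rate after stopping. The other is that the undercount will differ by arm: that would require early stopping without return to differ by arm, and the documents do not show it.

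The change is still worth making. It is nearly free, and the gap falls on subjects who stop and do not come back.

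**What to change.** In SAP 8.2.1 and Table 5, replace the last-visit bound with:
- **DB row:** within 30 days after the last DB application, or before the first open-label application, whichever is earlier.
- **Open-label rows:** within 30 days after the last open-label application.

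Apply it however the event was learned, at a visit or by phone. Whether the follow-up visit belongs to the period then no longer matters for TEAEs.

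Do not carry the open-label cut from SAP 8.1 into every row. The first open-label application always precedes the end of the open-label window, so in the open-label rows the clause would empty that window for the five switching arms. SAP 8.1 should say that the cut applies to DB summaries only.

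The cost is SAP wording and one small programming change, with no new data. AE counts may rise slightly.
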